### **6.14.2 Laboratory Data**

Descriptive statistics (n, mean, SD, median, min, max) of the observed values and change from baseline (continuous data) will be presented by treatment group (cohort, subcohort) and visit for each hematology, chemistry and urinalysis parameter.

Each measurement (continuous data) will be classed as below, within, or above normal range, based on ranges supplied by the laboratory used. Shift tables in relation to the normal range from baseline to the worst recorded result in each trial period will be presented.

In addition to central laboratory, platelet counts will be analyzed in local laboratory. This local laboratory data will be reported as part of the laboratory tables describe above.

All laboratory data will be listed.

Some laboratory samples are analyzed in local laboratory instead of central laboratory. If data from same sample is available from both central and local laboratory then the records from central laboratory will be used. Local laboratory might use different units and/or normal ranges to central laboratory and this need to be taken into account as described below.

For shift tables (low/normal/high) local lab data will use the original units and normal ranges.

For descriptive statistics, local laboratory results are normalized using location-scale normalization or scale normalization to be comparable to central lab results. These methods are described by Karvanen (2003).

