- g) Platelet counts will be assessed by the local as well as the central laboratory. If platelet clumping is observed in a local sample, the test should be repeated locally before IMP administration. In addition, a smear may be performed locally at the investigator's discretion.
- h) Only to be performed during the run-in period in case the screening laboratory results became available more than 12 weeks before the baseline visit.
- i) All parameters that are not described in a separate assessment in this Trial Schedule are to be performed by the central laboratory, as specified in Section 6.2.2.2.
- j) Coagulation parameters will be assessed by the local laboratory only.
- k) Only applicable for female subjects of child-bearing potential.
- l) Assessments should be performed in the order they are listed after all the questionnaires.
- m) To determine which muscle should be taken for muscle biopsies in this trial.

Further details will be described in the site manuals (e.g. Laboratory Manual, Site Operations Manual, Pharmacy Manual).

2) BASELINE AND SAD

BASELINE and SAD							
Trial Period	Single Dose Treatment						
Time Point: Day (D)	Day 0 or 1 ^{a)}	Day 1					
Time Point	Pre-dose/ Baseline	Pre-dose	0.5h after start of infusion	Immediately after end of infusion	1h after end of infusion	3h after end of infusion	7h after end of infusion
Time Window			±10 min	±10 min	±10 min	±10 min	±1h
Administrative							
Enrollment	✓						
Concomitant medications	✓						
Safety Assessments							
Physical examination ^{b)}	✓						
Vital signs (pulse rate, BP, RR, temperature, pulse oximetry)	✓ ^{c)}	✓ ^{d)}	✓ ^{d) e) f)}	✓ ^{d) e) f)}	✓ ^{d)}	✓ ^{d)}	✓ ^{d)}
Liver ultrasound including hepatic elastography	(✓) ^{g)}						
Platelet count ^{h)}	✓						
Clinical laboratory tests ^{i) u)}	✓						✓
Cardiac troponin ^{j)}	✓						
Complement assessments ^{i) j)}	✓				✓		✓
Coagulation assessments ^{k)}	✓						
Erythrocyte sedimentation rate ^{k)}	✓						
Urinalysis (dipstick)	✓						
Urine pregnancy test ^{l)}	✓						
Collect AEs/SAEs	✓						

BASELINE and SAD							
Trial Period	Single Dose Treatment						
Time Point: Day (D)	Day 0 or 1 ^{a)}	Day 1					
Time Point	Pre-dose/ Baseline	Pre-dose	0.5h after start of infusion	Immediately after end of infusion	1h after end of infusion	3h after end of infusion	7h after end of infusion
Time Window			±10 min	±10 min	±10 min	±10 min	±1h
PD/Exploratory Efficacy Assessments							
Blood sample for biomarkers (optional)	✓						

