6.2.2.2 Clinical Laboratory Tests

Clinical laboratory parameters should be monitored at the time points specified in the [TRIAL SCHEDULES](#).

In addition to testing of all parameters (except coagulation and erythrocyte sedimentation rate [ESR]) at the central laboratory, platelet counts will also be assessed locally prior to IMP administration and muscle biopsy. Platelet counts as determined by the local laboratory need to be within normal laboratory references ranges before IMP administration (at the time points specified in the [TRIAL SCHEDULES](#)), or before performing a muscle biopsy. The samples for platelet count verification cannot be older than 3 days. Any discrepancy between the results of the local and central laboratory should be discussed with the medical monitor before any further IMP administration. The coagulation panel and ESR will only be tested locally; they will NOT be repeated at the central laboratory. If thrombocytopenia is reported during the trial after the first IMP administration, and if an immature platelet fraction (IPF) test is available at the local laboratory, IPF test results should be obtained in addition to the platelet count. The IPF is the ratio of immature platelets to the total number of platelets, indicating the percentage of young, so-called 'reticulated' platelets.

All clinical laboratory assays will be performed according to the local or central laboratory's normal procedures. Normal reference ranges which are age- and gender-specific (as applicable) are supplied by the respective laboratories and used to assess the clinical laboratory data for clinical significance and out-of-range pathological changes. The investigator should assess out-of-range clinical laboratory values for clinical significance, indicating if the value(s) is/are not clinically significant or clinically significant.

The following clinical laboratory assessments will be performed:

Biochemistry:

General	Liver function tests	Kidney function tests	Other
- sodium	- AST	- BUN	Cardiac Safety - creatine kinase myocardial band (CK-MB)
- potassium	- ALT	- creatinine	- cardiac troponin
- chloride	- ALP	- cystatin C	
- calcium	- GGT	- eGFR ^{a)}	
- magnesium	- bilirubin: direct, indirect, and total		
- phosphorus	- albumin		Muscle injury
- bicarbonate	- total protein		- creatine kinase
- glucose	- bile acids		
- CRP			
- IgG and IgM			
- LDH			

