- a) Calculation of eGFR will be done by the central laboratory. The same method of calculation must be maintained for an individual subject.

Complement:

- C3	- C5a
- CBb	

Hematology:

- hemoglobin	- WBC differential ^{b)}
- hematocrit	- neutrophils
- red blood cell (RBC) count ^{a)}	- lymphocytes
- RBC parameters ^{a)} :	- monocytes
- mean corpuscular hemoglobin	- eosinophils
- mean corpuscular hemoglobin concentration	- basophils
- mean corpuscular volume	- platelet count ^{c)}
- white blood cell (WBC) count ^{b)}	- ESR

- a) RBC evaluation may include abnormalities in RBC count and/or RBC parameters and/or RBC morphology, which will then be reported by the laboratory.
- b) WBC evaluation may include any abnormal cells, which will then be reported by the laboratory. In addition, any other abnormal cells in a blood smear will also be reported
- c) If platelet clumping is observed in a local sample, the test should be repeated locally before IMP administration. In addition, a smear may be performed locally at the investigator's discretion.

Coagulation:

- PT ^{a)}	- INR
- aPTT	

- a) Depending on local laboratory's routine practice Coagulation panel test result may or may not include PT.

Urinalysis (dipstick):

- proteinuria	- hematuria
---------------	-------------

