9.11 Sample Size Justification

The sample size of 18 subjects treated with DYN101 is deemed to be appropriate to evaluate the safety and tolerability in a first-in-human trial. No power analysis was conducted to support the sample size.

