## Result Normalization

Location-scale normalization is used when both central lab and local lab have both lower and upper limits for normal specified in the data:

$$S_{\text{location-scale}} = L_S + (x - L_X) \frac{(U_S - L_S)}{(U_X - L_X)}$$

If location-scale normalization reaches negative value for a parameter then for that parameter scale normalized value will be used instead (giving priority for value using upper normal limit).

Scale normalization is used when either central lab or local lab have and only lower or upper limits for normal specified in the data (or location-scale normalization reaches negative value):

$$S_{\text{scale(upper)}} = x \frac{U_S}{U_x} \qquad \text{or} \qquad S_{\text{scale(lower)}} = x \frac{L_S}{L_x}$$

The notation in the above formulas are as follows:

- $s$  normalized result
- $x$  local laboratory result
- $L_X$  lower normal limit in local lab
- $U_X$  upper normal limit in local lab
- $L_S$  lower normal limit in central lab
- $U_S$  upper normal limit in central lab.

As a result of normalization the normalized values will be comparable to central lab results and are using the same units and normal ranges.

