### 6.14.3 Coagulation Data

Descriptive statistics (n, mean, SD, median, min, max) of the observed values and change from baseline (continuous data) will be presented by treatment group (cohort, subcohort) and visit for each parameter.

Shift tables in relation to the normality (Normal, Abnormal NCS, and Abnormal CS) from baseline to the worst recorded result in each trial period will be presented.

All data, including details of any abnormalities, will be listed.

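### Coagulation means by dose group pool values measured only at local laboratories, and the SAP has no step that makes them comparable; ESR falls under a normalisation rule that cannot be computed

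*SAP*

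**What the plan says.** **Comparability rule.** SAP 6.14.2 covers hematology, chemistry and urinalysis. It notes that a local laboratory might use other units or ranges than the central one, and for descriptive statistics "local laboratory results are normalized using location-scale normalization or scale normalization to be comparable to central lab results". The first formula applies under this condition: "Location-scale normalization is used when both central lab and local lab have both lower and upper limits for normal specified in the data". The fallback scales by one limit only, but that limit is again the ratio of a central to a local value; U_S is defined as the "upper normal limit in central lab" and L_S as its lower counterpart.

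**Where the tests are run.** Protocol 6.2.2.2: "The coagulation panel and ESR will only be tested locally; they will NOT be repeated at the central laboratory". The screening schedule agrees: "Coagulation parameters will be assessed by the local laboratory only". Each laboratory supplies its own reference ranges. ESR is listed in the protocol's hematology panel. For PT, the protocol adds: "Depending on local laboratory's routine practice Coagulation panel test result may or may not include PT".

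**What is summarised.** SAP 6.14.3 asks for "Descriptive statistics (n, mean, SD, median, min, max) of the observed values and change from baseline (continuous data", by cohort, subcohort and visit. It mentions neither normalisation nor units. Its shift tables use the categories normal, abnormal not clinically significant and abnormal clinically significant.

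**Outputs.** SAP Section 12 sends the coagulation descriptive table (14.3.5.4.1) and the mean-profile figure (14.3.5.4.1) to IDMC meetings 1 to 4. SAP Section 8 keeps the IDMC safety outputs in the abbreviated report after early termination.

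**The concern.** The SAP amendment table gives the reason for adding normalisation in version 3.0: to make laboratory parameters comparable across laboratories. Coagulation and ESR depend wholly on local laboratories, so they need such a step most, and neither gets a workable one.

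Protocol 3.5 plans 5 to 10 sites in Europe and the USA with 1 to 5 subjects each, and about 6 subjects per dose level. A dose group is therefore a small, uneven mix of sites. If laboratories report on different scales, a difference between doses in mean aPTT or PT can come from who was enrolled where. The protocol includes coagulation in regular safety monitoring (3.2.3) and ESR among the laboratory signals for vasculitis (7.2). Mean change from baseline in laboratory data by dose is a secondary endpoint.

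**Working it through.** **1. The amount of local-only data.** The trial has no power figure to reproduce ("No power analysis was conducted to support the sample size"). The stated figures that bear on this point are in Protocol Table 4: 31 coagulation and 30 ESR samples per subject up to MAD Week 25. Counting the schedule ticks:

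- Coagulation: screening 1 + baseline 1 + SAD follow-up 9 + MAD 13 + extension 7 = 31.
- ESR: the same without screening = 30.

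Both agree with Table 4. For 18 completing subjects this is 18 × 31 = 558 and 18 × 30 = 540 planned samples, with no central counterpart for any of them.

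**2. Can the rule be evaluated?**

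- Location-scale: s = L_S + (x − L_X)(U_S − L_S)/(U_X − L_X)
- Scale: s = x·U_S/U_X or s = x·L_S/L_X

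Without L_S and U_S, all three are undefined. For ESR this blocks the instruction in 6.14.2, and the SAP does not say whether the value is then used raw or left out. For coagulation the rule is not invoked at all, and 6.14.3 asks for observed values.

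**3. Possible size (assumed ranges; the documents give none).** Take six subjects, each at the middle of their own laboratory's range. Laboratory A has range 25–35 (middle 30), laboratory B has limits f times higher, and k of the six are at B. The raw mean shifts by (k/6)(f − 1):

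| f | k = 1 | k = 2 | k = 3 |
|---|---|---|---|
| 1.1 | 1.7% | 3.3% | 5.0% |
| 1.2 | 3.3% | 6.7% | 10.0% |
| 1.3 | 5.0% | 10.0% | 15.0% |
| 8 (unit-type mismatch) | 117% | 233% | 350% |

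**4. Two groups with different site mix (assumed aPTT ranges 23–32 s and 28–40 s).** Mid-range values are (23 + 32)/2 = 27.5 s and (28 + 40)/2 = 34 s.

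- Mix 4:2 gives (4 × 27.5 + 2 × 34)/6 = 29.67 s.
- Mix 2:4 gives (2 × 27.5 + 4 × 34)/6 = 31.83 s.
- The difference is 2.17 s, or 7.3%, with no drug effect.

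**5. Change from baseline.** In that example nobody changes, so mean change is zero in both groups and the offset cancels. A scale difference does not cancel. If every subject rises by the same proportion p, the mean changes are 29.67p and 31.83p, again 7.3% apart. A unit mismatch carries through in the same way.

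**6. As multiples of the local upper limit.** Mid-range is 27.5/32 = 0.859 at A and 34/40 = 0.850 at B. The 4:2 and 2:4 means are 0.856 and 0.853. The gap falls from 7.3% to about 0.4%.

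**The case against.** Several stronger readings are tempting, and the documents do not support them.

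- *A reader might infer that the SAP orders normalisation of coagulation and that the order fails.* Section 6.14.2 is written for hematology, chemistry and urinalysis, and 6.14.3 never calls on it. The failed instruction concerns ESR, through its place in the protocol's hematology panel. For coagulation there is simply no rule.
- *A reader might infer that laboratories do report in different units and ranges.* The SAP says only that they might. No coagulation or ESR range or unit appears in either document, and the number of laboratories is inferred from the number of sites.
- *A reader might take the 2.17 s as an expected bias, or as bias in the secondary endpoint.* It rests on assumed ranges and affects observed means only. In that example it vanishes from mean change.
- *A reader might infer that a real drift in one subject would be hidden from the IDMC.* At meetings 1 to 4 it also receives coagulation individual profiles (Figure 14.3.5.4.2), the shift table, the listing of abnormal laboratory values and the full coagulation listing. None of these depends on comparing laboratories.
- *A reader might infer that ESR will be pooled raw.* The SAP does not say.

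It is also fair to say that no numeric pausing or interruption rule in Protocol 7.11 uses coagulation or ESR, that platelets have central results, and that the trial is descriptive. These points limit the consequence. They do not answer why a mean by dose should be tabulated on scales that may differ between subjects when a scale-free alternative exists.

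**Conclusion.** The point holds, with a limited reach. For coagulation, the SAP orders pooled means, SDs, mean changes and mean profiles by dose group from local-only results with no comparability step; for ESR, it prescribes a step that cannot be computed. That no central limits exist is an inference from the tests never being run centrally.

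The effect is confined to the pooled summaries. Its size depends on ranges that the documents do not give: nil if all laboratories share units and ranges, a few percent to 15% of a group mean for ranges 1.1 to 1.3 times apart, and far more for a unit mismatch. A constant offset cancels in change from baseline; a scale or unit difference does not. Because these tables and figures are kept in the abbreviated report, the change is worth making.

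**What to change.** - **SAP 6.14.3:** summarise aPTT, and PT where it is reported in seconds, as result divided by the reporting laboratory's upper limit of normal, with change from baseline on that ratio. Summarise INR as reported. Show the number of subjects contributing to each PT summary, since not every site reports it.
- **SAP 6.14.2:** limit normalisation to tests that have central limits. State that ESR is presented in one common unit without normalisation, with its shift table by local range.
- **Fallback:** where a local limit cannot be obtained, use shift tables and listings only.

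The cost is a short SAP edit and a small derivation. Neither document shows that numeric coagulation limits are in the database, because the 6.14.3 shift tables use investigator categories. If they are not, they must be entered from the normal-value lists that sites already supply for local tests (Protocol 10.3). ESR and INR would still be pooled as reported, so their group means should be read with that in mind.

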## Result Normalization

Location-scale normalization is used when both central lab and local lab have both lower and upper limits for normal specified in the data:

$$S_{\text{location-scale}} = L_S + (x - L_X) \frac{(U_S - L_S)}{(U_X - L_X)}$$

If location-scale normalization reaches negative value for a parameter then for that parameter scale normalized value will be used instead (giving priority for value using upper normal limit).

Scale normalization is used when either central lab or local lab have and only lower or upper limits for normal specified in the data (or location-scale normalization reaches negative value):

$$S_{\text{scale(upper)}} = x \frac{U_S}{U_x} \qquad \text{or} \qquad S_{\text{scale(lower)}} = x \frac{L_S}{L_x}$$

The notation in the above formulas are as follows:

- $s$  normalized result
- $x$  local laboratory result
- $L_X$  lower normal limit in local lab
- $U_X$  upper normal limit in local lab
- $L_S$  lower normal limit in central lab
- $U_S$  upper normal limit in central lab.

As a result of normalization the normalized values will be comparable to central lab results and are using the same units and normal ranges.

### 6.14.3 Coagulation Data

Descriptive statistics (n, mean, SD, median, min, max) of the observed values and change from baseline (continuous data) will be presented by treatment group (cohort, subcohort) and visit for each parameter.

Shift tables in relation to the normality (Normal, Abnormal NCS, and Abnormal CS) from baseline to the worst recorded result in each trial period will be presented.

All data, including details of any abnormalities, will be listed.

### 6.14.4 Complement Data

Descriptive statistics (n, mean, SD, median, min, max) of the observed values and change from baseline (continuous data) will be presented by treatment group (cohort, subcohort) and visit for each parameter.

Each measurement (continuous data) will be classed as below, within, or above normal range, based on ranges supplied by the laboratory used. Shift tables in relation to the normal range from baseline to the worst recorded result in each trial period will be presented.

### **6.14.5 Vital Signs**

Descriptive statistics (n, mean, SD, median, min, max) for observed values and changes from baseline in the following vital signs will be presented by treatment group (cohort, subcohort) at each visit:

- Systolic blood pressure (mmHg)
- Diastolic blood pressure (mmHg)
- Pulse rate (bpm)
- Respiration rate (breath/min)
- Body temperature (degrees Celsius)
- Pulse Oximetry (SpO2)
- Body weight (kg)
- BMI (kg/m^2)

All vital sign data will be listed.

### **6.14.6 Electrocardiogram Data**

Descriptive statistics for observed values and changes from baseline in the following ECG variables will be tabulated by treatment group (cohort, subcohort) at each visit:

- Heart rate (bpm)
- PR interval (ms)
- RR interval (ms)
- QRS duration (ms)
- QT interval (ms)
- QTc interval (ms)

Shift tables in relation to the overall interpretation (Normal, Abnormal NCS, and Abnormal CS) from baseline to the worst recorded result in each trial period will be presented.

All ECG data, including details of any abnormalities, will be listed.

### **6.14.7 Physical Examination**

All data, including details of clinically significant findings will be listed.

At baseline and after 24 weeks of MAD treatment (Week 25 visit), the symptom-directed physical examination will include a neurological assessment. Neurological examination will be presented similarly to physical examination.

### **6.14.8 Liver Ultrasound and Hepatic Elastography**

The observed data for liver ultrasound and hepatic elastography assessments will be listed only.

## **7 INTERIM ANALYSIS**

Not applicable. Study was terminated before the interim analysis.

## **8 PRIMARY AND FINAL ANALYSIS**

The study was terminated early and therefore planned primary and final analyses will not be performed. Reporting will include only same set of outputs as was delivered for the IDMC meetings (full safety analyses) and selected key efficacy endpoints. Section 12 of this SAP is updated to highlight which outputs are excluded from the planned.

## **9 INDEPENDENT DATA MONITORING COMMITTEE ANALYSIS**

The purpose of the IDMC is to review study data of the cohorts, before proceeding to the next dose level. Further details about Independent Data Monitoring Committee (IDMC) meetings and deliverables are described in IDMC Charter. IDMC will be reviewing data at least 4 time during the study:

1. Organizational Meeting.
2. First Data Review Meeting
  - When last subject from SAD1 has completed study visit SAD1 W3 (Day 15).
3. Second Data Review Meeting
  - When last subject from SAD2 has completed study visit SAD2 W3 (Day 15)
4. Third Data Review Meeting
  - When at least two subjects in each sub cohort have passed study visit MAD1 W6 and all available SAD3 data available at the time of the meeting (SAD3 dosing is optional for this IDMC meeting)

#### 5. Fourth Data Review Meeting

- When last subject from MAD1 has completed study visit MAD1 W13 and last subject from MAD2 has completed study visit MAD2 W13

### **9.1 IDMC Open Session / Closed Session**

Separate outputs will be delivered for IDMC open and closed sessions.

Open session tables will be including only overall treatment group. Closed session reports will be including treatment groups (cohort, subcohort) and overall as defined in section [6.3](#) of this document.

## **10 CHANGES TO PLANNED PROTOCOL ANALYSIS**

Additional exploratory Bayesian analyses for MFM 32, continuous respiratory measures and continuous strength measures were added in section [6.13.10](#).

The study was stopped and the final reporting will be including only the IDMC outputs and selected efficacy parameters (FVC, MIP, Total MFM32 Score and PGI-C).

